#### 5.3.1 Pooling of Centers

Subjects from all centers will be pooled for all analyses.

#### 5.3.2 Adjustments for Covariates

Predose (baseline) PPR values will be included in the mixed model as the adjustment for covariate.

#### 5.3.3 Multiple Comparisons/Multiplicity

Not applicable.

#### 5.3.4 Examination of Subgroups

Not applicable.

#### 5.3.5 Handling of Missing Data, Dropouts, and Outliers

Missing values in PPR will not be imputed in this study.

For PD analyses, two summaries for the primary and secondary PPR endpoints will be produced, if different, one for all data in PD analysis set and one for all completers.

For safety summaries, all data in Safety Analysis Set will be included.

#### 5.3.6 Other Considerations

Not applicable.

## 5.4 Efficacy Analyses

Not Applicable.

## 5.5 Pharmacokinetic, Pharmacodynamic, Pharmacogenomic, and Other Biomarker Analyses

### 5.5.1 Pharmacokinetic Analyses

The Safety Analysis Set will be used for individual listings of E2082 plasma concentration-time data. The PK Analysis set will be used for descriptive statistics of E2082 plasma concentration-time data. Plasma concentrations will be tabulated by nominal sampling time and summarized by treatment group.

Various PK parameters will be derived and relationship between PK of E2082 and PD parameters will be explored. These analyses will be specified in separate PK SAP/report.

### 5.5.2 Pharmacodynamic Analyses

No multiplicity adjustments will be made. The PPR measurements collected at the 5 postdose timepoints on a given treatment day will be averaged and the arithmetic average value will be used for both primary endpoint and secondary endpoint analyses. The predose PPR data from the respective treatment period will be used as the baseline data for that period. The following PD analyses will be performed on the PD Analysis Set.

#### Primary PD Analyses

The reduction in PPR response will be evaluated for 8 hours postdose during each Treatment Period. A diminution in response is anticipated with the dose range.

The primary endpoint, mean change from baseline of the average PPR in the most sensitive eye condition, will be summarized by treatment group, and analyzed using a mixed effects model for crossover part of the study. The mixed effects model for the crossover part of the study will include treatment (E2082 2.5 mg, 25 mg, and placebo), period, and sequence as fixed effects, baseline (predose) measurement as a covariate, and subject nested within sequence as a random effect. Least squares (LS) means, difference in LS means of each E2082 dose (2.5 mg or 25 mg) compared to placebo, and 90% CIs will be presented with no adjustments for multiplicity.

#### Secondary PD Analyses

The secondary endpoints of mean change from baseline of the average PPR for each E2082 dose for all 3 different eye conditions (eye closure, eyes closed, and eyes open) will be summarized by treatment group and compared with placebo by using the same mixed effects model as for primary PD analyses.

Table and figure for the proportions of subjects with complete suppression, partial response, or no response will be displayed by treatment group (see [section 8.3](#) for definition of complete, partial suppression or no response).

Evaluation of onset, maximum change, and duration of photosensitivity response at each dose level will be performed for all 3 eye conditions for each treatment using summary and graphical displays.

Sensitivity analyses may be conducted for photosensitivity response, for example, in subjects who completed all 3 Treatment Periods 1 through 3 versus those who are included in the PD Analysis Set. Other exploratory analyses may be conducted as data permit.

All other PD data (ie, BL-VAS data) may be summarized by treatment groups using standard summary statistics.

PK-PD analyses may include examination of relationship between PK of E2082 and SPR (eg, time of onset, maximum change, and duration of response; and BL-VAS data) using model-based approaches as permitted by data. Details of the PK/PD analyses will be described in a separately prepared analysis plan and its report.

## 5.6 Safety Analyses

Evaluations of safety will be performed on the Safety Analysis Set. Safety data that will be evaluated include adverse events (AEs), clinical laboratory results, vital signs, ECGs, C-SSRS, and neurological/physical examinations.

Treatment-emergent adverse events (TEAEs) will be summarized for each treatment group by incidence of each AE.

Descriptive summary statistics of the laboratory, vital signs, and ECG parameters, and changes from baseline will be presented by treatment group. The proportion of subjects with any treatment-emergent report of suicidal ideation and behavior and intensity of these behaviors will be summarized.

Study Day 1 for all safety analyses will be defined as the date of the dose of study drug in treatment period 1.

### 5.6.1 Extent of Exposure

The number of subjects exposed to each study drug dose and placebo will be summarized descriptively by treatment group and treatment period.

### 5.6.2 Adverse Events

The AE verbatim descriptions (investigator terms from the CRF) will be classified into standardized medical terminology using the Medical Dictionary for Regulatory Activities (MedDRA). AEs will be coded to the MedDRA (Version 20.0 or higher) lower level term

(LLT) closest to the verbatim term. The linked MedDRA PT and primary system organ class (SOC) are also captured in the database.

A treatment-emergent adverse event (TEAE) is defined as an AE that emerges during treatment, having been absent at pretreatment (Baseline) or

- Reemerges during treatment, having been present at pretreatment (Baseline) but stopped before treatment, or
- Worsens in severity during treatment relative to the pretreatment state, when the AE is continuous.

Only TEAEs will be included in the summary tables. All AEs, treatment-emergent or otherwise, will be presented in subject data listings.

The TEAEs will be summarized by treatment group using the Safety Analysis Set. The incidence of TEAEs will be reported as the number (percentage) of subjects with TEAEs by SOC and PT. A subject will be counted only once within an SOC and PT, even if the subject experienced more than 1 TEAE within a specific SOC and PT. The number (percentage) of subjects with TEAEs will also be summarized by maximum severity (mild, moderate, or severe). The number (percentage) of subjects with TEAEs will also be summarized by relationship to study drug (Yes [related] or No [not related]).

The number (percentage) of subjects with treatment-emergent SAEs will be summarized by the latest edition of MedDRA SOC, and PT. A subject data listing of all SAEs, including deaths, will be provided. A subject data listing of all AEs leading to discontinuation from study drug will be provided.

### 5.6.3 Laboratory Values

Laboratory results will be summarized using Système International (SI) units, as appropriate. For all quantitative parameters listed in [protocol section 9.5.1.5.3](#), the actual value and the change from baseline to each postbaseline visit, and to the end of treatment (defined as the last on-treatment value at that dose) will be summarized by visit and treatment group using descriptive statistics. Qualitative parameters listed in [protocol section 9.5.1.5.3](#) will be summarized using frequencies (number and percentage of subjects), and changes from baseline to each postbaseline visit and to end of treatment visit via shift tables. Percentages will be based on the number of subjects with both nonmissing baseline and relevant postbaseline results.

Number and percentage of subjects with markedly abnormal laboratory values will be summarized. [Appendix 1](#) (Sponsor's Grading for Laboratory Values) below presents the criteria that will be used to identify subjects with treatment-emergent markedly abnormal laboratory values (TEMAVs). Except for phosphate, a TEMAV is defined as a postbaseline value with an increase from baseline to a grade of 2 or higher. For phosphate, a TEMAV was defined as a postbaseline value with an increase from baseline to a grade of 3 or higher.

Laboratory test results will be assigned a low/normal/high (LNH) classification according to whether the value was below (L), within (N), or above (H) the laboratory parameter's reference range and presented in the listings.

When displaying the incidence of TEMAVs, each subject may be counted once in the laboratory parameter high and in the laboratory parameter low categories, as applicable.

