### 9.1.2 Treatment Phase

The duration of the Treatment Phase will be 6 weeks and will include 3 blinded Treatment Periods for a randomized crossover design, followed by an Open-label Treatment Period.

Up to 3 concomitant AEDs ([Section 9.4.7](#)) are allowed during the course of the study, provided that the dosage of concomitant AED(s) has remained stable for at least 4 weeks or 5 half-lives, whichever is longer, before Screening. In the case where a new AED regimen has been initiated for a subject, the subject must be on the new AED for at least 8 weeks and the dose must have remained stable for at least 4 weeks or 5 half-lives, whichever is longer, before screening. During the study, changes to concomitant AEDs (including dosage) are not permitted unless medically necessary and upon consultation with the Sponsor. Adherence to a stable AED regimen is critical as missed doses or changes during the study may affect the subject's photosensitivity response.

The Screening Disposition case report form (CRF) page must be completed to indicate whether the subject is eligible to participate in the study and to provide reasons for screen failure, if applicable.

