### 9.3.1 Inclusion Criteria

Subjects must meet all of the following criteria to be included in this study:

1. Male or female 18 to 65 years of age at the time of informed consent.
2. A diagnosis and/or history of a PPR on EEG (ie, photosensitivity epilepsy).
3. If currently being treated with AED(s), up to a maximum of 3 concomitant AEDs is allowed provided that doses must have remained stable for at least 4 weeks or 5 half-lives, whichever longer, before Screening. In the case where a new AED regimen has been initiated for a subject, the subject must be on the new AED for at least 8 weeks before Screening and the dose must have remained stable for at least 4 weeks or 5 half-lives, whichever is longer, before Screening. (See [Exclusion Criteria No. 17-22](#) for AEDs that are exclusionary). (revised per Amendment 01)
4. Reproducible IPS-induced PPR on EEG of at least 3 points on the SPR scale in at least 1 eye condition (eye closure, eyes closed, eyes open) on at least 3 of the EEGs performed at Screening.
5. Body mass index (BMI) between 18 to 35 kg/m^2 (inclusive) and a total body weight greater than or equal to 45 kg at Screening.
6. Agrees to refrain from strenuous exercise and alcohol consumption during the 24-hour period before Screening and during the 24-hour period before each treatment day.
7. Willing and able to comply with all aspects of the protocol.

Note: Subjects who have completed the study per original protocol may re-enter the study provided that the subject meet inclusion criteria No. 2 to 7. (revised per Amendment 01)

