#### 9.7.1.5 Prior and Concomitant Therapy

All investigator terms for medications recorded in the CRF will be coded to an 11-digit code using the World Health Organization Drug Dictionary. The number (percentage) of subjects who took prior and concomitant medications will be summarized by treatment group, Anatomical Therapeutic Chemical (ATC) class, and World Health Organization Drug Dictionary preferred term (PT). Prior medications will be defined as medications that stopped before the dose of study drug. Concomitant medications will be defined as medications that started after the date of the dose of study drug up to 28 days after the subject's dose. All medications will be presented in subject data listings.

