### 5.2.5 Prior and Concomitant Therapy

Number (percentage) of subjects who took prior and concomitant medications, will be summarized by Anatomical Therapeutic Chemical (ATC) class and World Health Organization Drug Dictionary preferred term (PT).

Prior medications will be defined as medications that stopped before the dose of study drug in treatment period 1. Concomitant medications for a treatment group will be defined as medications that started after the date of the dose of study drug up to 28 days after the subject's dose or the next dose date in next treatment period, whichever is earlier.

Prior medications will be summarized overall and concomitant medications will be summarized by treatment group. The latest version before database lock will be used for analysis.

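### SAP 5.2.5 leaves continuing background AEDs out of both medication summaries, and SAP 5.6.3 does not say which dose a predose laboratory sample belongs to

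*SAP*

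**What the plan says.** **Medications.** SAP 5.2.5 gives two definitions: "Prior medications will be defined as medications that stopped before the dose of study drug in treatment period 1", and "Concomitant medications for a treatment group will be defined as medications that started after the date of the dose of study drug". The second window closes 28 days after the dose or at "the next dose date in next treatment period, whichever is earlier". Prior use is tabulated overall and concomitant use by treatment group. Protocol 9.7.1.5 has the same start-date rule: "Concomitant medications will be defined as medications that started after the date of the dose of study drug up to 28 days". It adds that every medication will be listed.

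**Who takes AEDs.** Protocol 9.3.1 allows up to 3 AEDs at stable doses. Where a regimen is new, "the subject must be on the new AED for at least 8 weeks before Screening". Protocol 9.1.2 adds that "changes to concomitant AEDs (including dosage) are not permitted unless medically necessary", and gives the reason: "Adherence to a stable AED regimen is critical as missed doses or changes during the study may affect" the subject's photosensitivity response.

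**Laboratory values.** SAP 5.6.3 provides that change from baseline to each postbaseline visit and to "end of treatment (defined as the last on-treatment value at that dose) will be summarized by visit and treatment group". Protocol 9.7.1.8.3 has the same rule without the reference to dose. Protocol 9.1.2.1 makes treatment-day laboratory tests predose only, and Table 6 places them between 2 hours and 30 minutes before dosing. SAP 8.2 defines each treatment period as one day.

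**Baseline for other measures.** SAP 5.3 and 8.1 use the last value before the Period 1 dose for everything except PPR. SAP 5.6.5 and protocol 9.7.1.8.5 ask for a time-matched QTcF change from baseline.

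**The concern.** The two medication rules do not cover all cases. A drug that began before the study and simply continued has not stopped before the first dose and has not started after any dose. In this population that is the normal pattern for antiepileptic treatment. The protocol itself calls these drugs concomitant AEDs, yet the SAP's definition of concomitant shuts them out. The table meant to describe background treatment would omit the drugs whose stability the protocol calls critical to the response being measured.

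The laboratory rule asks for a value that the schedule does not supply within a period, and the supplied text does not say what to use instead. Two programmers could produce different by-treatment tables of change and of markedly abnormal values (TEMAVs), and an abnormal result could be attributed to different doses.

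**Working it through.** The plan gives no figure of its own on this point, so the check applies its rules to its schedule. Nominal dose days are 1, 15, 29 and 43 (SAP 8.2).

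**1. Medication rules**

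Prior: stop date before the Day 1 dose. Concomitant for period *i*: start date after dose day *D(i)*, up to the earlier of *D(i)* + 28 and *D(i+1)*. The start-date windows are therefore after Day 1 to Day 15, after Day 15 to Day 29, after Day 29 to Day 43, and after Day 43 to Day 71 (43 + 28).

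Screening falls between Day −21 and Day −1. A new AED taken for at least 8 weeks (56 days) before Screening therefore started no later than Day −57 (−1 − 56). With Screening at Day −21, it started by Day −77 (−21 − 56).

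| Medication | Prior? | Concomitant? |
|---|---|---|
| AED started Day −77, ongoing | no | in none of the 4 periods |
| AED started Day −57, ongoing | no | in none of the 4 periods |
| Drug started on Day 1 after the dose | no | in none of the 4 periods |
| Drug started Day 5, ongoing | no | Period 1 only, though taken later too |
| Drug stopped Day −2 | yes | in none of the 4 periods |

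For a compliant subject, 0 of up to 3 unchanged background AEDs appear in either table. A drug started on a Visit 3 to 5 dose date is counted under the earlier treatment if the window includes its closing date, and is missed if it does not. The SAP does not say which.

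**2. Laboratory samples**

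Scheduled samples fall predose on Days 1, 15, 29 and 43 and at follow-up on Day 57. The number taken after a dose within its one-day period is 0 in each of the 4 periods. The Visit 2 sample serves as baseline (SAP 8.1). For *n* subjects and 3 blinded treatments there are 3*n* subject-treatment pairs:

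| Reading of the text | 9 subjects (27 pairs) | 6 subjects (18 pairs) |
|---|---|---|
| Sample belongs to the day's dose | 0 after that dose; 18 before it; 9 with the baseline sample only | 0; 12; 6 |
| Sample belongs to the preceding dose | 27 of 27 covered | 18 of 18 covered |

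Under the second reading the sample follows the dose by 14 days, or 11 to 17 with the ±3-day washout window. With the half-life of about 30 hours in protocol 7.1.2.1, half-lives elapsed = days × 24 / 30, which gives 8.8, 11.2 and 13.6 at 11, 14 and 17 days. Under first-order decay, 0.5 raised to those powers leaves about 0.22%, 0.04% and 0.008% of the drug. These samples can show effects that persist or appear about two weeks after a dose, not effects on the dosing day.

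**3. Baseline for BL-VAS, vital signs and ECG**

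The age of the baseline is the visit day minus Day 1: 0, 14, 28 and 42 days. With balanced sequences each blinded treatment averages (0 + 14 + 28) / 3 = 14 days, against 42 for 40 mg in Period 4. All three measures have a same-day predose value at every treatment visit (protocol 9.5.1.4.2 and Table 4). No 4-hour ECG is scheduled on an untreated day, so a time-matched change from the stated baseline cannot be formed. The changes above 30 and 60 msec can still be computed from a predose value.

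**The case against.** On medications, the omission is confined to summary tables. Protocol 9.7.1.5 lists every medication for about 9 subjects, so a reader can recover AED use by hand. That stands, and it limits the harm. A reader might infer that AED information is lost from the report; under the protocol it is not.

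On laboratory values, the stronger reading is that the SAP files results under a dose not yet given. The documents do not support that. The 0-of-27 count holds only if samples are labelled by visit, and the text does not fix that choice. SAP 5.2.5 already attributes medications from one dose to the next, and laboratory values can be read the same way. SAP Section 9 places derivation rules in separate documents, which were not supplied and may settle the matter. An unscheduled sample could also fall after a dose. What remains is an ambiguity that decides dose attribution, which is reason enough to settle it in the SAP.

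On the baseline, a reader might infer an error because PPR uses period-specific values and the other measures do not. The single baseline contradicts nothing, and a common baseline cancels in complete within-subject contrasts. The overlap of 40 mg with Period 4 comes from the design and would remain under any baseline. The vital-sign flags also require an absolute criterion. Whether predose readings at Visits 3 to 5 count as postbaseline is unstated. A reader might also infer inflated QTcF flag rates, but the documents give no QTcF variability from which to size this. Nor do they show whether the term time-matched or the baseline definition is the slip.

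**Conclusion.** The medication definitions are wrong as written. Applied literally, they leave every unchanged background AED out of both tables. This rests only on the stated rules and on compliance with the eligibility criteria; no assumed value is needed. An AED changed for medical necessity and recorded with a new start date could appear.

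The laboratory point is a gap, not a demonstrated error: no scheduled sample follows a dose within its period, and attribution is not stated in the supplied text. Misattribution is possible but not shown.

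The baseline choice and the QTcF wording are an inexpensive improvement to descriptive tables. The primary analysis, which uses each period's own predose PPR, is untouched by all of this.

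**What to change.** **SAP 5.2.5.** For each treatment, define concomitant as taken at any time from that dose date until before the next dose, or until 28 days after the dose if earlier, regardless of start date. Background AEDs then appear under every treatment during which they were taken. Align protocol 9.7.1.5, or record the change in SAP Section 7, which now states that the methods do not differ from the protocol.

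**SAP 5.6.3 and 8.2.** Assign each Visit 3 to 5 predose sample, and the follow-up sample, to the preceding dose. Drop the end-of-treatment value defined by dose. State that these samples reflect effects about 2 weeks (11 to 17 days) after dosing. Treat protocol 9.7.1.8.3 in the same way.

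**Optional.** In SAP 5.3 and 8.1, use each period's predose value as baseline for BL-VAS, vital signs and ECG, and do not count that value as postbaseline. In SAP 5.6.5, replace the time-matched QTcF change with change from same-day predose. Protocol 9.7.1.8.5 would then need alignment or a Section 7 entry.

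**Cost.** SAP wording and derivation programming, plus protocol clarification or, more simply, Section 7 entries. No new data are needed, because medication records reach back 3 months before Screening (protocol 9.4.7) and the predose values are already scheduled. The optional part adds reprogramming of the BL-VAS and safety change tables.

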#### 5.6.4 Vital Signs

Descriptive statistics for vital signs parameters (ie, systolic and diastolic BP, pulse, respiratory rate, and temperature) and changes from baseline will be presented by visit and treatment group.

In addition, the number (percentage) of subjects with at least 1 clinically notable vital sign results will be summarized by treatment groups. Clinically notable ranges are defined as follows:

Variable	Criterion value a	Change relative to baseline a
Heart rate	>120 bpm	Increase of $\geq 15$ bpm
	<50 bpm	Decrease of $\geq 15$ bpm
Systolic BP	>180 mmHg	Increase of $\geq 20$ mmHg
	<90 mmHg	Decrease of $\geq 20$ mmHg
Diastolic BP	>105 mmHg	Increase of $\geq 15$ mmHg
	<50 mmHg	Decrease of $\geq 15$ mmHg

a Clinically notable means that a value must have met both the criterion value and satisfied the magnitude of change relative to baseline.

Clinically notable vital sign values will be identified on the listings as those above (H) or below (L) a clinically notable range.

#### 5.6.5 Electrocardiograms

Descriptive statistics for ECG parameters and changes from baseline will be presented by visit and treatment group.

In addition, the number (percentage) of subjects with at least 1 postbaseline abnormal ECG result in QTc Fridericia during the treatment period will be summarized. Clinically abnormal ECG results in QTc Fridericia will be categorized as follows:

For the QT interval assessment, clinically abnormal ECG results for QT interval corrected for heart rate using Fridericia's formula (QTcF) will be categorized as follows: QTcF values >450 msec, >480 msec, and >500 msec, and time-matched change from baseline in QTcF >30 msec and >60 msec.

